Statistical Design and Power for Proposed Pilot Study 4:

The Care After Life-threatening Events (CALME) Study

ClinicalTrials.gov Identifier: NCT04589559

Document Date: 10/06/2020

Below we outline the statistical approach we will use to investigate the specific aims and associated hypotheses for this pilot study.

Aim 1: *To test the feasibility of a home-based heart rate variability biofeedback (HRVB) intervention in survivors of cardiac arrest (CA). Specifically, the primary purpose of this pilot study is to assess feasibility, acceptability, appropriateness, usability, and compliance for an at-home, 3-week HRVB intervention in 10 participants.*

Aim 1 will be tested by assessing the following measures:

(1) proportion of CA survivors eligible for this pilot study whom we approach and contacted who agree to participate in the trial of HRVB;

(2) proportion of participants who complete the outcome assessments at Visit 3;

(3) proportion of participants that complete a majority (≥ 8 of 15) of the at-home HRVB sessions;

(4) proportion of participants who report scores ≥ 4 for their final rating of the intervention's feasibility;

(5) proportion of participants who report scores ≥ 4 for their final rating of the intervention's acceptability;

(6) proportion of participants who report scores ≥ 4 for their final rating of the intervention's appropriateness for reducing anxiety;

and (7) proportion of participants who report total scores ≥ 68 for their final rating of the intervention's usability.

Statistical approach for Aim 1. In addition to computing the proportions listed above, we will conduct secondary analyses regarding measures 4, 5, and 6 (see above) as follows. A one-tailed t-test will be conducted comparing the mean for each scale against the comparison value of each 5-point scale's midpoint of 3.

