8 participants reported a mean of 4.75 ($SD = 0.46$). In a one-tailed t -test with a conservatively high comparison value of 4 (*Somewhat agree*), participants reported significantly *even more* strongly that they believed the HRVB intervention was appropriate for reducing anxiety, $t(7) = 4.58$, $p = .003$, Cohen's $d = 3.05$. This finding indicates that even just 8 participants were sufficient to detect an effect of HRVB on ratings of intervention appropriateness. This assessment is conservative given that the comparison value for the pilot data (4) was above the midpoint, whereas the comparison value for our Hypothesis 1A is the midpoint (3). The pilot data effect was detected with over 90% power, and we will require 80% power for this proposed pilot study. Therefore, we conservatively estimate that 10 participants will be sufficient to detect favorable ratings of intervention appropriateness. Similarly, we extend this rationale to the ratings of intervention feasibility and acceptability as well as usability.

Aim 2: *To assess whether cardiac-related interoceptive fear, anxiety and negative affect decrease from baseline to the 3-week visit and from baseline to the 6-week visit among CA survivors completing the HRVB intervention.*

Aim 2 will be tested by assessing the following measures:

- (1) Visit-2-to-3 change in cardiac-related interoceptive fear (measured as the within-person difference in the sum of the four cardiac-related items from the physical subscale of the Anxiety Sensitivity Index)*
- (2) Visit-2-to-3 change in trait anxiety (measured as the within-person difference in the total score of the trait version of the State-Trait Anxiety Inventory);*
- and (3) Visit-2-to-3 change in trait negative affect (measured as the within-person difference in the total score of the negative subscale of the Positive and Negative Affect Schedule).*

Statistical approach for Aim 2. We will test this aim by evaluating the change scores listed above. We hypothesize that the pattern of means will reveal a reduction in trait anxiety and negative affect. As mentioned above, this Phase-I trial is not powered to test the significance of these changes, nor is there a control comparison group to test whether the effects are caused by the HRVB intervention in this feasibility pilot study.

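### Is it a fault that the rating t-tests compare the mean with the midpoint of 3, when Aim 1 counts scores of 4 or more?

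*SAP*

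**What the plan says.** SAP, Aim 1, lists seven measures. Measures 4 to 6 each take the form "proportion of participants who report scores ≥ 4 for their final rating" of one attribute: feasibility, acceptability or appropriateness for reducing anxiety. No target is set for any of these proportions, and the SAP does not name 4 as the boundary of a favourable rating.

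SAP, Statistical approach for Aim 1, then adds to the proportions: "we will conduct secondary analyses regarding measures 4, 5, and 6 (see above) as follows". The test is specified as "A one-tailed t-test will be conducted comparing the mean for each scale against the comparison value of each 5-point" scale's midpoint, given as 3.

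The sample-size text of the SAP introduces the test as one of a difference from the midpoints. It supports the choice of 10 participants with earlier data from eight patients on one 5-point item, where 3 was the neutral response and 4 was mild agreement. Those data were tested "with a conservatively high comparison value of 4". The text then says explicitly that the planned comparison value is the midpoint, 3, and concludes that 10 participants suffice to detect favourable appropriateness ratings. It extends this reasoning to the other scales.

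Protocol, section 2 (Measures), says that acceptability, feasibility and appropriateness are each measured with a four-item scale. Neither document states how the items are combined.

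**The concern.** The same three scales seem to be held to two standards: 4 or more for each participant in the proportions, and anything reliably above 3 for the mean in the test. The earlier data used for planning were tested against the stricter value, so the planned test looks like a step down. The word favourable, applied to what the test detects, adds to that impression.

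The stake would be a misleading headline. Protocol, section 1, says the pilot data will influence the decision to seek funding for a large randomised trial. If lukewarm ratings produced a small p-value that was read as endorsement, while few or no participants scored 4 or more, that decision could rest on the wrong result.

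**Working it through.** **Inputs.** From the SAP: N = 10; one-sample, one-tailed t-test; comparison value 3; earlier data n = 8, mean 4.75, SD 0.46, tested against 4; required power 80%. Assumed: one-sided alpha 0.05, because none is stated.

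**Formulas.** t = (mean − c)/(SD/√n), where c is the comparison value. The smallest significant mean is c + t(0.95, n−1) × SD/√n. Power comes from the noncentral t distribution with noncentrality √n × (mean − c)/SD.

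**The SAP's own figures.** Six scores of 5 and two of 4 give mean 4.75 and SD 0.463, so t(7) = 0.75/(0.463/√8) = 4.58, as stated. Power against 4 at n = 8 is 99.3%, so the statement of over 90% holds. The printed p = .003 fits a two-sided test (0.0025; one-sided 0.0013), and the printed d of 3.05 does not follow from 0.75/0.46 = 1.63. Neither affects this point.

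**Can the test and the proportion diverge?** Yes. With t(0.95, 9) = 1.833, the smallest significant mean against 3 is:

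- SD 0.46: 3 + 1.833 × 0.46/√10 = 3.27
- SD 0.7: 3.41
- SD 1.0: 3.58

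If each four-item scale is scored as an item mean (an assumption), scores move in steps of 0.25. Five scores of 3.25 and five of 3.50 then give mean 3.375, SD 0.132, t(9) = 0.375/(0.132/√10) = 9.0 and p < .0001, with 0 of 10 at 4 or more. If scores were whole numbers this could not happen: with nobody at 4, the mean is at most 3. Seven 3s and three 4s would still give t(9) = 1.96, p = 0.041, with 30% at 4 or more.

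**Would a comparison value of 4 align them?** No. Against 4 the mean must reach 4 + 1.833 × 0.46/√10 = 4.27 at SD 0.46. Take eight 4s and two 5s: mean 4.2, SD = √[(8 × 0.04 + 2 × 0.64)/9] = 0.422, t(9) = 0.2/(0.422/√10) = 1.5, one-sided p = 0.084. All 10 participants are at 4 or more and the test fails. A proportion at or above a cut and a test of whether the mean exceeds that cut are different quantities, so some mismatch exists whichever value is chosen.

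**Power at N = 10.**

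| True mean | SD | Against 3 | Against 4 |
|---|---|---|---|
| 4.75 | 0.46 | >99.9% | 99.9% |
| 4.75 | 1.0 | >99.9% | 71% |
| 4.5 | 0.46 | >99.9% | 94% |
| 4.5 | 0.6 | >99.9% | 78% |
| 4.25 | 0.46 | >99.9% | 48% |

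The change is nearly free only if the earlier mean of 4.75 carries over with a small SD. That mean came from a single item, after in-clinic training, in eight patients with acute coronary syndromes. This study uses four-item scales after three weeks at home in cardiac arrest survivors.

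**The case for a change.** The strongest case on the other side is that divergence is not confined to contrived data. With a true mean of 3.5 and SD 0.46, simulation on quarter-point scores gives significance in about 93% of trials. Significance with fewer than half of participants at 4 or more occurs in about 89%, and with none at 4 or more in about 8%. Since the proportions have no target, the t-test is also the only yes/no result for these scales, and a reader may give it more weight than its secondary label warrants.

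The figures stand, on the assumption of item-mean scoring. What they show is that the test does what it is built to do: a true mean of 3.5 is above neutral, and a test against neutral should detect it. The modest proportion at 4 or more would be reported for the same participants, and nothing in the SAP lets the p-value override it or makes it the rule for the grant decision. It is fair to say that favourable is a loose word for a mean above 3, and that above neutral would be more exact. That bears on how a result is described and changes no result.

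**Conclusion.** The concern does not hold. The plan reports the proportion at 4 or more as its Aim 1 measure and adds a test against the neutral point, which it labels secondary and whose comparison value it states openly. It describes the 4 used on the earlier data as deliberately strict. These are two different questions, and both are answered on the same participants.

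The test against 3 can be significant with few participants at 4 or more, from a mean of 3.27 at SD 0.46. A test against 4 can equally fail with 10 of 10 at 4 or more (p = 0.084), and its power is 48% to 78% in plausible settings where the SAP requires 80%. Choosing between the two values is a trade-off on which competent statisticians may differ. This rests on one-sided alpha 0.05 and N = 10; the 0-of-10 case also needs item-mean scoring. The only residue is that a significant result should be read as above neutral.

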We will recruit 10 participants who each recently survived a cardiac arrest and who are either 1) participating in a separate ongoing longitudinal study (Cardiac Arrest Neuropsychological Outcomes Evaluation [CANOE]; IRB Protocol #: AAAR8497) or 2) on a mailing list to receive information from the Sudden Cardiac Arrest Foundation (SCAF), a community of cardiac arrest survivors, their families, and other advocates. They will complete a brief set of screening questions to determine eligibility. They will complete three “Video Visits” that will be conducted by study staff who will meet with the participant via the Zoom application associated with Columbia University Irving Medical Center, 1) an enrollment video visit within 72 months since their cardiac arrest, 2) a baseline/pre-intervention video visit approximately a week after the enrollment video visit (once participant confirms receiving study materials), and 3) a post-intervention video visit 3 weeks after the pre-intervention video visit. The first video visit will last approximately 45 minutes, the second video visit will last approximately 60 minutes and the third video visit will last approximately 30 minutes.

Upon obtaining verbal consent, the first video visit includes demographic and partner/caregiver questionnaires, download of the smartphone app (Elite HRV), and selection of appropriate chest strap size for the heart rate monitor for the participant.

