The second video visit consists of attachment of the heart rate monitor (Polar H10), setup of the smartphone app (Elite HRV), completion of questionnaires (cardiac-related interoceptive fear, trait anxiety, and trait negative affect), a short baseline resting state breathing task, and a training in how to do the intervention using the heart rate monitor together with the smartphone app. Since the equipment is unobtrusive and handled exclusively by the participant, this visit is easily conducted remotely. The hardware device (Polar H10 heart rate monitor) measures HR and HRV, and the app (Elite HRV) receives data wirelessly via a Bluetooth connection. During the second video visit, a heart rate monitor chest strap will be attached around the torso along the bottom of the rib cage of each participant to measure interbeat intervals in order to compute heart rate (HR) and heart rate variability (HRV). Participants will complete a paradigm in which they breathe at a set frequency (e.g., one breath lasting 10 seconds) while they watch their real-time heart rate on a visual display on the Elite HRV app. Participants will be told that the goal of the training is to increase the amount of variation in their heart rate between one heartbeat and the next heartbeat. Participants will have the advantage of seeing real-time HR feedback as a means to guide their success at maximizing HRV with each breath as the training progresses over time. Detailed procedures are provided to the IRB in separate documents entitled “CALME_HardwareAndAppInstructions_IPHONE.pptx” and “CALME_HardwareAndAppInstructions_Android.pptx.”

The third video visit consists of attachment of the heart rate monitor (Polar H10), a short baseline resting state breathing task, and completion of the self-report measures of cardiac-related interoceptive fear, trait anxiety, and trait negative affect. Within-in person changes in these measures will be computed as a preliminary test of the intervention’s efficacy.

Measures

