Cardiac-related interoceptive fear is measured with the four cardiac-related items from the Anxiety Sensitivity Index-3.[17] Trait anxiety is measured using the State-Trait Anxiety Inventory.[18] Cognitive and somatic facets of trait anxiety are measured with the State-Trait Inventory of Cognitive and Somatic Anxiety (STICSA).[18] Facets of trait affect are measured with the Positive and Negative Affect Schedule (PANAS)[19]. Those measures above are administered at both the pre- and post-training video visits. Additionally, at the post-training video visit only, participants complete the following standalone self-report items: 1) “How

pleasant did it feel to pay attention to your heart's activity during the training sessions at home?" (scale of 1, *very unpleasant*, to 5, *very pleasant*); 2) "How successful were you in increasing the variability in your heart activity by the end of the training sessions at home?" (scale of 1, *not at all successful*, to 5, *very successful*). Also at the third video visit, intervention usability is measured with the System Usability Scale, [20] and intervention acceptability, feasibility, and appropriateness are measured with the three validated four-item scales.[21] Additionally, we assess demographic information and partner and caregiver status.

3. Study procedures

Recruitment/First Video Visit (45 Minutes)

For participants already enrolled in the CANOE Study:

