Members of the study team will introduce participants to the heart rate monitor they received by mail and train them in its proper application. Participants put on the heart rate monitor and wear it for the duration of the session. Participants are also introduced to the Elite HRV app (previously installed in the 1st Video Visit). The experimenters assist participants in the app setting on their smartphones and pair the heart rate monitor via Bluetooth with the app. They complete the pre-intervention questionnaires to assess cardiac-related interoceptive fear, trait anxiety, and positive and negative trait affect. A two-minute resting-state reading is recorded using the "Elite HRV" app while participants sit in a comfortable, relaxed, and well-supported position with their feet flat on the floor. They then complete a single HRV biofeedback training session (see details below). Participants are trained in how to export the data on the app to an email with the form of *[name]* where ### is a study ID that pertains only to the participant in question and does not include any identifying information. HRV data are exported once via the app at the end of this session. Participants are made aware that they will be compensated for this session on their PayCard.

HRV Biofeedback Training (15 at-home sessions; 10 minutes each)

Participants are asked to complete the HRV biofeedback training with the heart rate monitor and app once per day for 10 minutes each time (at least 5 minutes) for at least 5 days each week. They are encouraged to practice the training before bedtime because it has been shown to improve HRV during sleep when practiced at that time. However, they are told that they can do the training at any time of day that works well for them.

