The post-training procedures are identical to the pre-training procedures except for the following elements. First, participants do not need to re-download the Elite HRV app, and participants are not re-trained in the use of the heart rate monitor and app because they are already familiar with them. Second, the participants will not complete the HRV Biofeedback training task (they will only complete the resting state task). Third, the self-report items about participants’ perceptions of the intervention are administered only at the post-training visit. Fourth, the session concludes with a short debriefing in which participants have a chance to share any feedback about completing the intervention and about the study in general. Fifth, participants will delete the study account in the Elite HRV App from their phones so that the study will not continue to receive their data following study completion.

4. Compensation

Participants receive a Bank of America PayCard in the mail after successfully completing the initial/first video visit (45 minutes). Once they confirm receiving the PayCard with study personnel, \$30 will be uploaded to the card as compensation for the first video visit. Following successful completion of the second 60-minute pre-intervention video visit, they will be compensated an additional \$60 on the PayCard, and following the third and final 30-minute post-intervention video visit they will be compensated an additional \$60 on the PayCard. Therefore, the total possible compensation for completing the study is \$150. All compensation is loaded onto one Bank of America PayCard registered specifically to the participant.

In addition, participants will be permitted to keep the study-provided heart rate monitor (Polar H10) upon completion of the study, which has an estimated value of \$70.00 when purchased as new.

5. Eligibility

For participants already enrolled in the CANOE Study:

Inclusion criteria

- (1) Age 18 years or older
- (2) Fluent in English
- (3) A diagnosis of cardiac arrest (CA)
- (4) Time elapsed since their CA is less than 72 months
- (5) Previously enrolled in the protocol titled “Cardiac Arrest Neuropsychological Outcomes Evaluation” (CANOE; IRB-AAAR8497)
- (6) Willing to be contacted about other studies (this applies to CANOE participants who agreed to be contacted about future research opportunities either during the initial consent process or during a follow-up visit or phone call)

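### Does the 6-week contrast named in SAP Aim 2, for which no visit exists, require a change to the plan?

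*SAP*

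**What the plan says.** The opening sentence of Aim 2 in the SAP sets out two contrasts for cardiac-related interoceptive fear, anxiety and negative affect, asking whether they "decrease from baseline to the 3-week visit and from baseline to the 6-week visit".

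The protocol's Study Design section schedules three video visits. Visit 1 is enrollment. Visit 2 is the baseline visit, about a week later, once the materials have arrived. Visit 3 is "a post-intervention video visit 3 weeks after the pre-intervention video visit". On content, "the first video visit includes demographic and partner/caregiver questionnaires" together with the app download and strap sizing, while Visit 3 includes "completion of the self-report measures of cardiac-related interoceptive fear, trait anxiety, and trait negative affect". The Measures subsection says of the outcome scales: "Those measures above are administered at both the pre- and post-training video visits". The Compensation section describes the third visit as the last one.

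Below the Aim 2 sentence, the SAP lists three measures, each a within-person change from Visit 2 to Visit 3. The paragraph on the statistical approach for Aim 2 says the aim is tested by evaluating those listed change scores. It adds that the trial is not powered to test them and has no control group.

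**The concern.** A formal aim names a time point that the study never reaches. Read literally, half of the aim cannot be reported, so the results would have to depart from it. Someone comparing the report with the SAP could not tell whether the 6-week clause was a drafting leftover or a planned follow-up that was dropped or left unreported.

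A 6-week assessment would also answer a different question. With training lasting 3 weeks, it would show whether any change persisted about 3 weeks after training stopped. The protocol says the pilot will inform a grant application for a larger randomized study, so a reader might want to know whether persistence was ever meant to be assessed.

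**Working it through.** The plan gives no power, alpha or sample-size figure that depends on this point, so the check is a visit calendar and a count of contrasts.

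**Calendar (protocol, Study Design).** Take Visit 2, the labelled baseline, as week 0.
- Visit 1: about week -1.
- Visit 3: week 3.
- Shortfall against a 6-week visit: 6 - 3 = 3 weeks.
- Counting from enrollment instead, Visit 3 falls at about 1 + 3 = 4 weeks, which is still not 6. Slow mail could delay Visit 2 and stretch that interval. But Aim 2 counts from baseline, and Visit 1 collects none of the Aim 2 outcomes.
- The SAP names the 3-week and 6-week visits separately, so Visit 3 cannot be both.

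**Contrasts (SAP, Aim 2).**
- Implied by the aim sentence: 3 outcomes x 2 contrasts = 6 changes.
- With a scheduled measurement: 3 outcomes x 1 contrast (Visit 2 to 3) = 3.
- Without one: 6 - 3 = 3.

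**What the analyst is told to compute.**
- Listed Aim 2 measures: 3, all Visit 2 to 3 changes.
- Aim 2 analysis: those 3 and nothing else.
- Exploratory Aim 2 correlations: the HRV slope against the same 3 changes.
- Aim 1 retention measure: completion of outcome assessments at Visit 3.

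**Effect of removing the 6-week words.** Change scores computed before: 3. After: 3. The visits, questionnaires, participants (N = 10) and Aim 1 proportions all stay the same.

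**Facts that fit but do not settle it.**
- Training is asked for "for at least 5 days each week", and 5 x 3 = 15 matches the 15 home sessions. That agrees with the 3-week intervention in SAP Aim 1, but a follow-up questionnaire would not need training to continue.
- Payments of 30 + 60 + 60 = 150 dollars equal the stated total, but an unpaid questionnaire would not show there.
- Participants delete the app account at Visit 3 "so that the study will not continue to receive their data following study completion". That concerns heartbeat-interval exports, not questionnaires.

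The absence of a 6-week assessment rests on the visit schedule, the timing of the questionnaires and the Aim 2 measure list.

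**The case for a change.** The strongest case for a change is that an aim should match its design. Three of the six implied changes have no visit, measure or analysis. Correcting the sentence would cost almost nothing, and leaving it invites doubt about a missing follow-up. The clause is in the current SAP text. The aim, its measure list and its analysis paragraph are all intact, so redaction or text extraction does not explain it.

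The factual part of this stands: the inconsistency exists, and neither document says how the clause got there. The inference to a needed change is weaker. The operative text directly below the aim fixes the time points, leaving no competing analysis to choose between and no room for selective reporting among measured outcomes. The count of three missing changes is one absent visit seen through three outcomes. It measures no bias, loss of precision or error rate. The doubt about a dropped follow-up is answered by the protocol's own schedule, which ends at Visit 3.

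Adding a real 6-week assessment would be a substantive change, needing a protocol amendment and up to 10 further questionnaire contacts. Nothing else in the documents indicates that one was planned, and the pilot's primary purpose, feasibility in Aim 1, does not need it.

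**Conclusion.** The observation is correct, but its weight is editorial. One clause in the Aim 2 sentence refers to a visit that appears nowhere else in either document. The listed measures, the Aim 2 analysis, the exploratory analysis and the protocol schedule all agree on Visit 2 to Visit 3, so the analysis is determined and can be carried out. No computed result changes: the three change scores, the Aim 1 measures and N = 10 are the same with or without the clause. Whoever next edits the SAP could align the sentence with the schedule, but no result or conclusion depends on it.

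This rests on two assumptions: that the measure list and analysis paragraph govern what is computed, as the SAP says, and that no 6-week assessment exists outside the two documents. If one had in fact been intended, the gap would lie in the protocol's visit schedule, not only in this sentence. The documents give no sign of that beyond the clause itself.
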